This is an open-label single-arm pilot clinical trial testing the feasibility, acceptability, and effects of a 4-week EC substitution intervention in 30 current smokers. Approach: Participants will be asked to switch from CC to the NJOY ACE electronic cigarette (EC) for 4 weeks. They will receive counseling to develop a plan to fully substitute CC for EC and to increase EC adherence. Follow-up assessment at 8 weeks will determine whether participants continue to use EC, return to cigarette smoking, or use both products. The primary outcomes are study feasibility (participant enrollment and retention) and change in cigarettes per day from baseline to week 4 (primary outcome). Secondary outcomes include change in exposure biomarkers (expired air CO, urine cotinine and anabasine) from baseline to week 4, product acceptability and tolerability (days of EC use, adverse events) and change in CC and EC use after EC provision ends. At the end of EC provision (week 4), we will conduct exploratory qualitative exit interviews in a purposive subsample to explore their experiences participating in the study and switching from CCs to ECs.

4. Subject Selection

Inclusion Criteria

- a) Participants in the Screen Assist study (IRB#2018P000539) who self-reported smoking cigarettes at the end of the study and were asked to complete a subsequent Screen Assist survey to ascertain their potential interest in a research study to test the effects of switching from CC to EC. Individuals who expressed interest in a future research study about EC on that survey are eligible for this study.
- b) Smoked ≥ 5 cigarettes/day in past month
- c) Willingness to try switching to EC for 4 weeks
- d) Own a mobile telephone
- e) Smoking status at study entry confirmed by breath carbon monoxide (CO) ≥ 6 ppm
- f) English speaking
- g) Willingness to travel to the MGH main campus for 3 in-person visits

Exclusion Criteria

- a) Plan to quit smoking and have set a quit date in the next 30 days
- b) Current EC use on >2 days in the past 30 days
- c) Hospitalization for acute coronary syndrome, unstable angina, CHF, stroke, pneumonia or COPD/asthma exacerbation in the past 1 month
- d) Be willing not to smoke marijuana in the 24h before each study visit

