6. STUDY PROCEDURES

	Phone Screening	EC Provision					F/U Phone Call
		In person screening / In Person Baseline	Phone Call	In person Visit	Phone Call	In Person Visit	
	-14	Week 0	Week 1	Week 2	Week 3	Week 4	Week 8
Screening and Enrollment							
Tobacco history since survey completion: past 30-day CC and EC use, plan to quit smoking in the next 30 days	X						
Other screening items	X						
Breath Carbon Monoxide		X					
Baseline Measures							
Current medical history		X					
Alcohol use screening		X					
CC and EC Use							
Recent CC quit attempts		X	X	X	X	X	X

Mass General Brigham Institutional Review Board
Intervention/Interaction Detailed Protocol

Current CC Use: Past 7-day use (Yes vs.no) and 7-day timeline follow back interview (TLFB)		X	X	X	X	X	X
Current EC use: Past 7-day use (Yes vs.no) and 7-day timeline follow back interview (TLFB)		X	X	X	X	X	X
EC pod collection/count				X		X	
Nicotine, CC, and EC Perceptions							
Absolute and comparative health and addiction risk perceptions of EC, CC and Nicotine		X				X	X
EC Acceptability							
E-Cigarette Sensory Effects and Appeal Ratings				X		X	
Electronic cigarette rating scale				X		X	
Electronic Cigarette Smoking Consequences Questionnaire				X		X	
Readiness to switch to EC							
Electronic cigarette taste and feel compared to cigarette				X		X	
Dependence, Withdrawal and Craving							
Time to first cigarette, number of cigarettes smoked per day; short-form PROMIS Nicotine Dependence Item Bank		X		X		X	
Penn State e-cigarette dependence index				X		X	
Minnesota Nicotine Withdrawal Scale (MNWS)		X		X		X	
Brief Questionnaire on smoking urges		X		X		X	X
Biomarkers							
Breath carbon monoxide (CO)		X		X		X	
Urine Cotinine		X		X		X	
Urine Anabasine		X		X		X	
Adverse events							
Adverse events			X	X	X	X	
Respiratory symptoms: American Thoracic Society questionnaire		X	X	X	X	X	
Exit qualitative interview							X

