Selection and provision of electronic cigarettes: Participants will receive a two-week supply of the NJOY ACE e-cigarette (NJOY, LLC). This product was selected because it is a 4th generation nicotine salt-based pod EC and is a commercially available consumer product that was granted a Premarket Tobacco Product Authorization (PMTA) from the FDA's Center for Tobacco Products (CTP) in 2022. This authorization required that FDA CTP decide that the product met the standard of being "appropriate for the protection of the public health," defined as it having net public health benefits that exceed its net public health risks. A tobacco product with a PMTA designation is not considered by FDA CTP to be an investigational device and does not need to obtain certification from the CTP's Investigational Tobacco Products (ITP) Program when it is used in a research study. We have confirmed the accuracy of this statement with an email communication with [name] of the FDA CTP's IPT Program (dated July 11, 2024).

The NJOY ACE contains a device and sealed pods available with 5% nicotine and is tobacco flavored. Each pod is equivalent to ~20 cigarettes, and participants will receive an EC pod supply equivalent to their average cigarette smoking rate at baseline. The supply of pods provided will be adjusted as needed to ensure the adequate amount to substitute cigarette use.

Participants will receive written and verbal instructions on how to use the device and be provided with written educational materials used in previous research trials to help vapers quit smoking. They will be instructed to use the EC instead of their usual CC brand, encouraged to switch completely to the EC by the end of the first week and try to use only the EC for the rest of EC provision period. All devices and pods will be labeled for investigational use only. Dispensing and collection logs will be used to track devices and pods. We will collect and count used and unused pods at visits.

Schedule of Assessments:

- a) Initial Phone Screening: Telephone screening will determine initial eligibility. Initial screening will query on all inclusion and exclusion criteria, except for CO. For those who meet the initial eligibility criteria, a research assistant (RA) will explain the purpose and procedures of the study, provide information on confidentiality, answer questions, and invite participant for an in-person final eligibility visit.

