- b) Baseline visit (Consent, Final eligibility, baseline data collection and product provision): Participants will receive a study overview. Informed consent for the study will be obtained. Final in-person eligibility will be confirmed with an exhaled carbon monoxide via Bedfont Micro Smokerlyzer. Participants meeting final eligibility will be enrolled in the study. Baseline data collection will immediately follow screening at the same visit. Measures will be completed per the schedule of measures above (see Table 1), broadly including: recent CC and EC use, cigarette dependence; respiratory symptoms; intentions to quit smoking; and biomarkers of tobacco use and inflammation. Biological assessments involving urine sample collection will be performed by the RA.
Following completion of all scheduled measures, participants will be provided with a complimentary NJOY ACE device, information on its storage and use, and disposable cartridges in the tobacco flavor. Participants will be provided with a number of pods comparable to 150% of their weekly consumption of nicotine based on their responses to the baseline timeline follow-back (TLFB). This quantity will ensure that participants have adequate pods to fully substitute combustible cigarettes within a reasonable margin of error (e.g., timing/scheduling of the next session) should they choose to do so. As each standard 5% NJOY ACE pod provide an amount of serum nicotine delivery in ideal use conditions comparable to one pack of cigarettes (i.e., 20 cigarettes), we will compute participants' average weekly cigarette consumption in packs and provide 1.5x that number of cartridges.
- c) Phone call visits at Weeks 1 and 3: These visits will be conducted by phone. Participants will be assessed for their cigarette, tobacco, and EC use. Participants will also be assessed for any quit attempt or adverse event and will be asked for any issues using the product and reminded to use the EC instead of the CC every time they want to smoke.
- d) In person Visit at Week 2: Participants will attend an in-person visit at Week 2 to receive a new 2-week supply of pods, return used and unused pods to measure EC use, complete assessments and troubleshoot device or other study-related issues.
- e) In person Visit at Week 4: Participants will attend an in-person visit at Week 4 when product provision will end and all baseline assessments will be repeated.

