There is a possible direct benefit to participants. Patients will be instructed to reduce their combustible daily cigarette use and to substitute e-cigarette use for cigarette use. This aims to facilitate reductions in cigarettes smoked per day, reduced tobacco smoke exposure and eventual increase in health benefits (e.g., improvement in dyspnea). Even if e-cigarettes are found to not reduce exposure to toxins, cigarettes per day, or if respiratory symptoms were to worsen with their use (which is not anticipated), this study will still provide valuable data about the need for patients to avoid e-cigarette products. The data from this trial will be clinically informative and inform policies on regulating and marketing e-cigarettes. A systematic review of randomized controlled trials indicates that e-cigarettes are more effective than nicotine replacement products for helping cigarettes smokers to quit smoking.¹⁰ Quitting smoking is associated with a rapid reduction in tobacco-related health risks, even in older individuals who have smoked enough to qualify for lung cancer screening, as our study population does.⁴¹

In the qualitative interview, participants will also discuss their attempts to reduce their cigarette use and barriers and facilitators to e-cigarette substitution which may be useful for increasing participants' awareness of their cigarette use, what maintains use, and obstacles to stopping use which could be useful for eventual cessation of cigarette use.

9. Statistical Analysis

Aim: Assess the feasibility, acceptability, and short-term effects of providing ECs for 4 weeks to encourage switching from cigarettes to e-cigarettes by individuals who did not quit after smoking cessation treatment provided in the context of LCS and do not currently plan to quit.

Hypothesis 1: (i) ≥ 40% of eligible smokers who are offered trial enrollment. (ii) ≥ 75% of enrollees complete the trial

Primary Outcomes H1: Study enrollment (% screened of those who completed our study 1 survey, % eligible of those screened; % enrolled of those screened eligible); retention (% of patients who complete the trial, defined as completing the final follow-up assessment and >50% of the study visits). We will also document reasons for ineligibility and exclusion to inform future trial protocols.

Analysis H1: Descriptive statistics using data from study recruitment and enrollment records will test hypotheses.

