H2b: Participants will report fewer CPD at the end of the 4-week EC switch period, relative to their baseline values.

Primary Outcome H2: Change in mean cigarettes smoked per day (CPD) between baseline and 4 weeks.

Analyses H2: Paired sample t-tests will be used to compare mean differences in past 7-day CC use from BL to Week 4. Linear mixed models will also be used to test differences in CPD and CO levels over the study period (using data from all observed time points observed). Primary analysis will be conducted among completers and multiple imputation will be used for a sensitivity analysis.

Additional Planned Analyses: Analyses of other secondary outcomes will include EC acceptability measures and changes from baseline to week 4 in the levels of: EC use days, levels of biomarkers of exposure (CO, anabasine, cotinine). The qualitative interviews will be audio-recorded, transcribed, and iteratively analyzed using the framework method of content analysis (both inductive and deductive) in Dedoose 8.3 qualitative software. The trained research assistants will separately review each transcript and develop a coding framework. The coders will meet weekly with the PIs to review results for agreement.

Power: If 40% (n=30) of 75 screened eligible subjects agree to participate, the width of the 95% CI will be limited to 11.1% on each side. If at least 24 of the 30 subjects complete the study, the width of the 95% CI will be limited to 14.7% on each side. Hyp 2b: Participants will report fewer CPD after 4 weeks of EC provision relative to their baseline values. Results from PI [name]'s recent study⁴² found a significant reduction in mean CPD in the EC arm (N=18) from 14.8 cigarettes per day to 4.4 in week 4 (Change SD: 3.81) (p-value <0.01) (Cohen's d=1.6). With a sample size of 30 and a 25% attrition rate, we expect at least 24 of the 30 subjects will provide data on CPD reduction. The study will have 80% power to detect a more conservative Cohen's d of 0.60 with a two-sided type-I error of 5%. A Cohen's d of 0.60 will translate into a mean change of 3 CPD (SD of change=5).

10. Monitoring and Quality Assurance

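### The primary cigarettes-per-day analysis is tied to undefined completers, so weeks 1–3 data from people who miss week 4 do not inform it, although an all-time-points mixed model is already planned

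*Combined protocol and SAP*

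**What the plan says.** The primary H2 outcome is the change in mean CPD between baseline and week 4 (Section 9, Primary Outcome H2). Under Analyses H2 the plan gives a paired t-test of past-7-day cigarette use, then a linear mixed model for CPD and CO "using data from all observed time points observed", and then this sentence: "Primary analysis will be conducted among completers and multiple imputation will be used for a sensitivity analysis". It does not say whether the restriction applies to the t-test only or also to the mixed model. It defines no H2 completer and states no missing-data assumption.

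Two other places bear on who a completer is:

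- The Power paragraph of Section 9 assumes a "sample size of 30 and a 25% attrition rate, we expect at least 24 of the 30 subjects will provide data on CPD reduction". This suggests that a completer is someone with baseline and week-4 CPD.
- The only written definition of completing is for retention under H1: "defined as completing the final follow-up assessment and >50% of the study visits". The last scheduled assessment is the week-8 phone call. Section 3 gives its purpose: "Follow-up assessment at 8 weeks will determine whether participants continue to use EC".

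The schedule table in Section 6 lists "Current CC Use: Past 7-day use (Yes vs.no) and 7-day timeline follow back interview (TLFB)" at weeks 0, 1, 2, 3, 4 and 8, so CPD is measured three times between baseline and the primary time point. Participants are "encouraged to switch completely to the EC by the end of the first week and try to use only the EC" for the rest of the provision period. The primary time point coincides with the end of provision: "Participants will attend an in-person visit at Week 4 when product provision will end".

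**The concern.** A baseline-to-week-4 comparison in completers gives no weight to people who miss week 4, even where up to three weekly CPD values show how they were doing. In a single-arm study no control group shares the same loss, so any link between leaving and CPD change goes straight into the estimate. The background section intends the results as preliminary data for a fully powered RCT, so a distorted reduction could carry over into that trial's assumptions.

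The undefined term adds a smaller problem. The analysis set could be settled after the data are seen, and the restriction sits awkwardly beside a mixed model said to use every observed time point.

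**Working it through.** **1. The plan's own figure.** Inputs from the Power paragraph: mean change 3, SD of change 5, so d = 3/5 = 0.60; n = 24; two-sided 5%. Paired t-test: df = 23, noncentrality = 0.60 × √24 = 2.94, power 80.4%. The stated 80% reproduces, and no stated figure is disputed here. With all 30 contributing, power would be 88.8%.

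**2. Expected loss.** 24 of 30 is 6/30 = 20% loss; the same sentence says 25%. That mismatch is a separate matter; here it only gives the range 20–25%.

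**3. What each reading leaves out of the primary estimate.**

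- *Completer = baseline and week-4 CPD.* No week-4 value is lost. With 6 people missing week 4, up to 6 × 3 = 18 CPD values from weeks 1–3 are unused.
- *Completer = the H1 retention definition.* The same values are unused. In addition, a person with week-4 CPD who misses the week-8 call loses an observed baseline/week-4 pair.

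**4. Size without a dropout model.** Suppose 24 completers average a reduction of 3 and the 6 others average m. The mean over all 30 is (24 × 3 + 6m)/30:

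- m = 3: 3.0
- m = 1.5: 2.7
- m = 0: 2.4
- m = 4.5: 3.3, so the completer figure would then be too low.

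**5. Size under an assumed dropout model.** From the plan: SD of change 5 and true reduction 3.0. Assumed, because the documents give nothing: normal changes, and logistic loss with slope b = 0.5 or 1.0 log-odds per SD, calibrated to 20% overall. Let p be a person's probability of loss and ρ the correlation between the week-4 change and the change that drives loss. Then

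completer bias = ρ × SD × b × E[p(1−p)] / (1 − loss).

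Numerical integration gives E[p(1−p)] = 0.154 for b = 0.5 and 0.139 for b = 1.0.

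- b = 0.5: 5 × 0.5 × 0.154/0.8 = 0.48 × ρ
- b = 1.0: 5 × 1.0 × 0.139/0.8 = 0.87 × ρ

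*Loss depends on an earlier observed change.* With ρ = 0.5 to 0.9, completers show 3.24–3.43 at b = 0.5 and 3.43–3.78 at b = 1.0. An estimate that also uses the earlier value shows 3.00. Simulations over weeks 0–4 under three covariance structures (baseline SD 6 assumed; lost people seen through week 1, 2 or 3 with equal chance) agree: completers 3.23–3.38 and 3.42–3.69, unstructured mixed model 2.98–3.02.

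*Loss depends on the week-4 change itself* (ρ = 1). Completers show 3.48 and 3.87. The mixed model shows 3.15–3.32 and 3.25–3.59, a partial correction.

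*Opposite sign* (those who reduce most leave more often; loss on the week-4 change). Completers show 2.52 and 2.13.

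*Some leave before week 1.* With one third of the lost leaving before the week-1 call, depending on their unseen week-1 change, and the rest as in the first case, the mixed model shows 3.02–3.17 against 3.2–3.7 for completers.

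**6. Power.** In simulation with 20% unrelated loss and d = 0.60, power was 81% for completers and 81–85% for an unstructured mixed model. These runs used a sequential-regression covariance estimate followed by generalised least squares, and normal CPD. They do not test the convergence of a standard unstructured fit at N = 30.

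**The case against.** The plan already contains most of the remedy. The mixed model uses all observed time points and multiple imputation is a planned sensitivity analysis. A reader might infer that the weeks 1–3 data are discarded altogether. The documents do not support that: those data are outside the primary estimate only. What remains is which planned analysis carries the primary result, and an undefined term.

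A reader might also infer that a missed week-8 call removes week-4 data. The retention definition makes that possible, but it was written for H1, H2 ends at week 4, and the power text counts people who provide CPD data. It is the weaker reading, and one clause settles it.

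A third tempting inference is that the CPD reduction will be overstated. The documents give no reasons for leaving, and Section 6 (Remuneration) does not tie payment to product use, which may limit selective loss. If loss is unrelated to CPD change, the completer mean is unbiased.

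The illustration also depends on chosen inputs. Slopes, correlations, baseline SD and exit times are assumed. Where loss depends only on observed values, a correctly specified mixed model is right by construction. The instruction to switch by the end of week 1 makes early CPD plausibly informative but does not show that it predicts week 4. At N = 30 and slope 0.5, the simulated bias of 0.25–0.36 CPD is about a third of the standard error (5/√24 = 1.02). Root mean squared error was 1.04–1.07 for completers and 0.96–1.01 for the all-data estimate; at slope 1.0 it was 1.08–1.22 and 0.97–1.03.

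All of this limits the size and certainty of the bias. It does not justify leaving the primary set undefined, or leading with the analysis that ignores data already being collected.

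**Conclusion.** The point holds as a worthwhile and inexpensive improvement. The primary H2 analysis rests on completers, undefined for H2. On the likelier reading, weeks 1–3 CPD from people who miss week 4 does not inform the primary estimate. On the less likely reading, some observed week-4 pairs are dropped as well.

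The size is conditional. With 20% loss driven by an earlier observed change and slopes of 0.5–1.0 log-odds per SD, a true reduction of 3.0 appears as about 3.2–3.8 in completers and about 3.0 in an all-observed likelihood estimate. This is an illustration, not a forecast. The sign could be reversed, there is no bias if loss is unrelated to CPD change, the gain shrinks if people leave before week 1, and it is only partial if loss depends on the unobserved week-4 value. Confidence is high on the wording gap and low on the size of any bias in this 30-person pilot.

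**What to change.** Make the already planned linear mixed model the primary H2 analysis and specify:

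- all enrolled participants with baseline CPD;
- every observed CPD value at weeks 0–4, regardless of week-8 status;
- week as a categorical factor, with week 4 minus baseline as the primary contrast;
- a prespecified covariance structure with small-sample inference;
- the missing-at-random assumption, stated in words.

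Keep the paired t-test as supporting, in everyone with baseline and week-4 CPD. Keep the planned multiple imputation, with weeks 1–3 CPD in the imputation model. Use the definition under Primary Outcomes H1 for retention only.

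If the t-test stays primary, the minimum is one sentence: H2 completers are participants with baseline and week-4 CPD, and the restriction does not apply to the mixed model.

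The cost is analysis-plan wording and slightly more analysis work, with no new data. The downsides are reliance on a model at N = 30, where zero CPD in full switchers may strain the normality assumption, and possibly a less favourable estimate.

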Summary of the literature gap and impact. Older long-term smokers who are eligible for LCS are a high priority population for tobacco cessation.²¹ However, they are less likely than younger smokers to quit smoking even with evidence-based smoking cessation interventions. They could benefit from tobacco harm reduction strategies, which could be offered in the context of LCS. However, the acceptability and efficacy of tobacco harm reduction strategies among older smokers is not known.²¹ This project will fill this critical literature gap. Studies such as the one we propose are needed to assess older smokers' perceptions of risk and benefits related to EC, their willingness to substitute CC with EC and to assess if EC can serve as a harm reduction tool for smokers at high risk for lung cancer who are unable to quit. If so, ECs could be incorporated as part of harm reduction and cessation interventions offered to smokers in the context of LCS. The information gained will also provide critical preliminary data to support a future application to test, in a fully powered RCT, whether switching from CC to EC could reduce tobacco-related health risks for older smokers.

2. Specific Aims and Objectives

Aim: Assess the feasibility, acceptability, and short-term effects of providing ECs for 4 weeks to encourage switching from cigarettes to e-cigarettes by individuals who did not quit after smoking cessation treatment provided in the context of LCS and do not currently plan to quit.

Hyp 1: (i) > 40% of eligible smokers who are offered participation in the trial will enroll. (ii) > 75% of enrollees complete the trial.

Hyp 2: Participants will report fewer CPD at the end of 4 weeks of EC provision, relative to their baseline values.

3. General Description of Study Design

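### None of the planned H2 analyses shows the cigarette reduction if participants relapse unobserved and miss Week 4; one return-to-baseline sensitivity analysis would fill the gap cheaply

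*Combined protocol and SAP*

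**What the plan says.** Section 9 (Statistical Analysis) of the combined protocol and SAP defines the H2 primary outcome as "Change in mean cigarettes smoked per day (CPD) between baseline and 4 weeks". Three analyses bear on it.

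- **Primary test.** "Paired sample t-tests will be used to compare mean differences in past 7-day CC use from BL to Week 4", run among completers.
- **Mixed model.** "Linear mixed models will also be used to test differences in CPD and CO levels over the study period". Every available assessment enters this model. It is not labelled a sensitivity analysis, but it does use partial data from people who leave early.
- **Named sensitivity analysis.** "Primary analysis will be conducted among completers and multiple imputation will be used for a sensitivity analysis". The imputation model, its predictors and its missing-data assumption are not stated.

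Nowhere do the documents set missing Week 4 CPD to baseline, shift imputed values by a delta, or make any other missing-not-at-random assumption.

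The schedule table in Section 6 collects a 7-day timeline follow-back of cigarette use at Weeks 0, 1, 2, 3, 4 and 8. The Power paragraph of Section 9 expects at least 24 of 30 participants to provide CPD data, and gives attrition as 25%.

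**The concern.** Participants did not quit after cessation treatment and have no current plan to quit. New pods are handed out in person at Week 2. A plausible route to missing Week 4 data is therefore that someone stops using the device, resumes usual smoking and stops attending.

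If that relapse falls after the last recorded contact, the observed data carry no trace of it. The completer analysis leaves the person out. The mixed model and a missing-at-random imputation predict Week 4 from earlier reports and from attenders with similar reports. All three can then overstate the reduction in the same direction.

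What is at stake is mainly the size of the reported effect. The background says the study will "provide critical preliminary data to support a future application to test, in a fully powered RCT", so the estimate will be read as well as the p-value.

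**Working it through.** **Inputs** (Section 9, Power paragraph): 30 enrolled; mean change 3 CPD; SD of change 5; two-sided 5%; stated power 80%. The number without Week 4 CPD is 6 (from 24 of 30) or 7 to 8 (25% of 30 = 7.5).

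**1. The plan's own figure.** Paired t-test with n = 24 and d = 3/5 = 0.60: noncentrality = 0.60 × √24 = 2.94, 23 degrees of freedom. Power is 80.4%, which agrees with the stated 80%.

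**2. Mean if every dropout is back at baseline.** With k dropouts at zero change, mean = (30 − k) × 3 / 30.

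- k = 6: 24 × 3 / 30 = 2.4, which is 20% below 3.0
- k = 7: 23 × 3 / 30 = 2.3, which is 23% below
- k = 8: 22 × 3 / 30 = 2.2, which is 27% below

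**3. Spread and test result.** Let s be the SD of change among dropouts. The variance over all 30 is

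[(30 − k − 1) × 25 + (30 − k) × 9 + (k − 1) × s² − 30 × mean²] / 29.

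For k = 6 and s = 5: (575 + 216 + 125 − 172.8) / 29 = 743.2 / 29 = 25.63, so SD = 5.06, d = 2.4 / 5.06 = 0.47 and t = 0.474 × √30 = 2.60.

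| Dropouts | s | Mean | SD | d | p |
|---|---|---|---|---|---|
| 6 | 0 | 2.4 | 4.62 | 0.52 | 0.008 |
| 6 | 5 | 2.4 | 5.06 | 0.47 | 0.015 |
| 7 | 5 | 2.3 | 5.08 | 0.45 | 0.019 |
| 8 | 5 | 2.2 | 5.09 | 0.43 | 0.025 |

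For comparison, 24 completers alone give 3.0 (95% CI 0.89 to 5.11, p = 0.007). The s = 0 row fills in exact zeros, which shrinks the SD artificially. The s = 5 rows are closer to imputing around baseline with spread.

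**4. Allowance for imputation.** The s = 5 rows treat imputed values as if observed. Rubin's rules add a between-imputation variance of (k/30)² × 25/k.

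- k = 6: 25.63/30 + 0.167 = 0.854 + 0.167 = 1.021; t = 2.4/√1.021 = 2.38
- k = 8: 25.96/30 + 0.222 = 0.865 + 0.222 = 1.088; t = 2.2/√1.088 = 2.11

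With many imputations and small-sample degrees of freedom, (30/32) × 29 × (1 − between/total), about 22.7 and 21.6, p is about 0.026 and 0.047. The result stays below 0.05, with little to spare at 8 dropouts.

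**5. How far dropouts must worsen.** Treating the filled-in values as observed, significance is lost only if dropouts smoke above baseline: by about 2.6 CPD (6 dropouts) or 1.6 CPD (8 dropouts) with no spread, and by about 2.1 or 0.9 CPD with SD 5.

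**The case against.** The strongest reply is that the plan already does a good deal. CPD is recorded at Weeks 1, 2 and 3, and the mixed model uses every observed time point. Someone who resumes smoking, says so at one of those contacts and then leaves is partly captured, and the imputation would capture them too if it uses those weeks. This stands. Completer and missing-at-random analyses would differ when relapse is observed, so a reader should not infer that agreement among the three would be uninformative. The gap is limited to relapse after the last contact.

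It is also fair to say that the document does not state a missing-at-random assumption. That reading is an inference from what unspecified multiple imputation usually means.

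A reader might infer from 3.0/2.4 = 1.25 and 3.0/2.2 = 1.36 that the reported reduction will be 25 to 36% too large. The documents do not support that as a general statement. It needs every dropout to be at zero change on average, and the upper end needs 22 completers where the plan expects at least 24. If dropouts kept half the reduction (1.5 CPD, an assumption), the mean would be (24 × 3 + 6 × 1.5)/30 = 2.7 or (22 × 3 + 8 × 1.5)/30 = 2.6.

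A reader might also turn the fall in d into a sample-size penalty for the later trial. The background promises preliminary data, but does not say that this within-person change will size that trial.

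Finally, this is a 30-person single-arm pilot that reports retention, so a reader could work out the return-to-baseline mean unaided. That lowers the priority. It does not supply the interval, or fix the assumption before data are seen.

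**Conclusion.** The gap is real and modest, and closing it is a cheap improvement. Multiple imputation is the only named sensitivity analysis and is unspecified. The mixed model also relies on missing at random. No planned analysis therefore shows the reduction under relapse that the observed data do not foreshadow.

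At the plan's values, the illustration lowers the estimate from 3.0 to between 2.2 and 2.4 CPD. This rests on 6 to 8 dropouts, all back at baseline on average, and on completers showing the planned 3 CPD with SD 5. It is a scenario, not a forecast. A reader might infer that the H2 conclusion is at risk. At these values it is unlikely to change, although the margin is thin with 8 dropouts once imputation uncertainty is counted. The benefit is a more honest range for the size of the reduction.

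**What to change.** Keep the completer analysis and the multiple imputation. In Section 9, under the H2 analyses:

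- State that the imputation uses baseline and Weeks 1 to 3 CPD and assumes missing at random.
- Pre-specify one return-to-baseline analysis of all enrolled participants. Impute missing Week 4 CPD around the person's own baseline, with spread, and combine the results by Rubin's rules. State the spread in advance.
- Report that estimate and its 95% CI beside the completer estimate.

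A short range of delta shifts is optional, since at the planning values significance is lost only if dropouts smoke more than at baseline.

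The cost is a sentence or two in the plan and a small extra analysis on data already collected. No visits or measurements are added. The downside for the sponsor is that a less favourable estimate appears alongside the primary one.
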